9.2 Serious Adverse Events

A serious adverse event (SAE) is any untoward medical occurrence that at any dose meets 1 or more of the following criteria:

- Is fatal
- Is life threatening
 - Note: Life-threatening refers to an event that places the patient at immediate risk of death. This definition does not include a reaction that, had it occurred in a more severe form, might have caused death
- Requires or prolongs in-patient hospitalization
- Results in persistent or significant disability or incapacity

Page 46

- Is a congenital anomaly or birth defect, that is, an AE that occurs in the child or fetus of a patient exposed to IP prior to conception or during pregnancy
- Is an important medical event or reaction.

For this study, a generalized tonic-clonic convulsion/seizure is to be considered an SAE.

Any SAE, whether or not considered related to study drug, must be reported within 24 hours of knowledge of the event by forwarding (fax, email) the study-specific SAE Report Form to Catalyst. The Investigator should not wait to collect information that fully documents the SAE before notifying Catalyst. As additional information becomes available, including but not limited to the outcome of the SAE and any medication or other therapeutic measures used to treat the event, it must be reported within 24 hours in a follow-up report to Catalyst.

The Investigator should follow all unresolved SAEs until the events are resolved or stabilized, the patient is lost to follow-up, or it has been determined that the study treatment or participation is not the cause of the AE. Resolution of AEs (with dates) should be documented in the eCRF and in the patient's medical record.

For some SAEs, Catalyst may follow up by telephone, fax, email, and/or a monitoring visit to obtain additional case details deemed necessary to appropriately evaluate the SAE report (e.g. hospital discharge summary, consultant report, autopsy report).

At the last scheduled visit, the Investigator should instruct each patient to report any subsequent SAEs that the patient's personal physician(s) believes might be related to prior study treatment.

The Investigator should notify Catalyst of any death or SAE occurring at any time after a patient has discontinued, or terminated study participation, if felt to be related to prior study treatment. Catalyst should also be notified if the Investigator should become aware of the development of cancer, or of a congenital anomaly, in a subsequently conceived offspring of a patient that participated in this study.

Reporting of SAEs to the IRB will be done in compliance with the standard operating procedures and policies of the IRB and with applicable regulatory requirements. Adequate documentation must be provided showing that the IRB was properly and promptly notified as required.

Page 47

9.3 Safety Blood Collection

Patients who experience a serious or severe AE should have, at the discretion of the Investigator, a blood sample drawn for safety labs as soon as possible after the AE.

Additional blood sampling may be performed at any time during the study if warranted to monitor patient safety.

9.4 Pregnancy

Pregnancy in a patient or partner should be reported within 24 hours of the site becoming aware of the pregnancy by fax or email of the Pregnancy Report Form in the study reference materials to Catalyst. In addition, pregnancy in a patient is also reported on the End of Study CRF. The Investigator must make every effort to follow the patient through resolution of the pregnancy (delivery or termination) and to report the resolution on the follow-up form (Pregnancy Report Form: Additional Information) in the study reference materials. In the event of pregnancy in the partner of a study patient, the Investigator should make every reasonable attempt to obtain the woman's consent for release of protected health information.

9.5 Urgent Safety Measures

The regulations governing clinical trials state that the sponsor and Investigator are required to take appropriate urgent safety measures to protect subjects against any immediate hazards that may affect the safety of subjects, and that the appropriate regulatory bodies should be notified according to their respective regulations. According to the European Union (EU) Clinical Trial Directive 2001/20/EC (and consistent with the US FDA regulations at 21 CFR 56.108(a)), "...in the light of the circumstances, notably the occurrence of any new event relating to the conduct of the trial or the development of the investigational medicinal product where that new event is likely to affect the safety of the subjects, the sponsor and the Investigator shall take appropriate urgent safety measures to protect the subjects against any immediate hazard. The sponsor shall forthwith inform the competent authorities of those new events and the measures taken and shall ensure that the IRB/EC/REB is notified at the same time." The reporting period for urgent safety measures is the period from the time of signing of the ICF through the completion of the last study visit. Investigators are required to report any urgent safety measures with 24 hours.

Page 48

Examples of situations that may require urgent safety measures include discovery of the following:

- An immediate need to revise IP administration (i.e. modified dose amount or frequency not defined in protocol).
- Lack of study scientific value, or detrimental study conduct or management.
- Discovery that the quality or safety of IP does not meet established safety requirements.

10 APPROPRIATENESS OF MEASUREMENTS

The measures of safety used in this study are routine clinical procedures. The efficacy measures use a variety of approaches to evaluate changes in neuromuscular function and muscle strength. These standardized tests have been previously used for determination of response to therapeutic intervention in patients with MG and in other indications and, thus, are relevant for use in this study in patients with LEMS.

11 STUDY PROCEDURES

11.1 Screening Visit

An ICF must be signed and dated by the patient, the Investigator or designee, and witness (if required) before any study-related procedures are performed.

After patient has signed an ICF, they will be screened for enrollment into the study. The study activities listed below will be performed during the 7 days that constitute the Screening Visit.

Informed Consent.

Page 49

- Assessment of Inclusion/Exclusion criteria
- Demographics (sex, race, ethnic origin, age)
- Medical history, including allergy history and number of hospitalizations or ER visits in last 6 months.
- History of orthopedic procedures that may affect walking or getting up out of a chair
- Method of LEMS diagnosis
- Complete physical examination including weight and height
- Vital signs (seated position), including systolic blood pressure (SBP), diastolic blood pressure (DBP), heart rate, and body temperature
- Liquid biopsy specimen (if patient opts for cancer screening)
- Urine pregnancy test in females of childbearing potential only
- Assessment of AEs/SAEs
- Assessment of concomitant medications

11.2 Randomization Visit (Study Day 0)

The study activities listed below will be performed on Study Day 0, while the patient has been on open-label amifampridine phosphate and in relationship to the usual dosing schedule.

Assessment	Start Time After Dose* (+ 10 minutes unless otherwise specified)
SGI	40 minutes
Patient most bothersome symptom, Question 1	Following SGI
QMG	Following patient symptom evaluation
3TUG	Following QMG

^{*}Administration of medication represents Time 0 (minutes)

- Assessment of AEs/SAEs
- Assessment of concomitant medications

Patients who are deemed eligible will be dispensed double-blind study medication (amifampridine phosphate or placebo tablets) on Study Day 0, according to the treatment group to which they are randomized. The patient's open-label amifampridine must be collected. Patients must stop their open-label amifampridine and will start to take the blinded study

Page 50

medication beginning with the next scheduled dose after all assessments on open-label medication have been completed.

Patients must be instructed that they are not to take any doses of their prior, open-label amifampridine during the study and not to change pyridostigmine dose or schedule.

11.3 End of Treatment (Study Day 4)

Patients will take their blinded study medication on Days 1-3. On Day 4, a dose of blinded study medication must be administered by the site study personnel. This is the same medication that the patient has been taking on Days 1-3. The assessments listed below will be performed **following either the second, third, or fourth dose of medication to be taken on Day 4, and this should be the same dose that assessments on Day 0 were subsequently performed.** For example, if the patient took their second dose of amifampridine in the clinic on Day 0 and had assessments started 40 minutes later, then on Day 4, that patient should be assessed after taking their second dose of medication in the clinic, starting 40 minutes after the dose.

Safety assessments (vital signs and AEs/SAEs) should be performed before study personnel give the dose of blinded medication. Concomitant medications should be reviewed for any changes. A urine sample, to determine amifampridine level, should be collected on Day 3 (after patient has taken a dose of blinded medication), and on Day 4, before study personnel give the dose of blinded medication.

Assessment	Start Time After Dose* (+ 10 minutes unless otherwise specified)
SGI	40 minutes
Patient most bothersome symptom, Question 2	Following SGI
QMG	Following patient symptom evaluation
CGI-I (compared to Day 0)	Following QMG
3TUG	Following CGI-I

^{*}Administration of medication represents Time 0 (minutes)

Page 51

The container of blinded study medication dispensed on Study Day 0 must be returned to study personnel and the IP Accountability form completed to determine if the blinded study medication doses were taken.

This represents the end of the study.

11.4 Early Discontinuation Visit

Any patient that discontinues from the study, regardless of the reason, will be requested to complete all Early Discontinuation visit assessments/procedures as listed below after the last dose of study medication. Every reasonable effort should be made to contact any patient who is lost to follow-up.

In cases of Early Discontinuation, medication will have been stopped some time prior to seeing the patient for the below assessments. The date and time of the last dose of medication should be recorded in relation to when the assessments are performed.

- Assessment of AEs/SAEs
- Vital signs
- Concomitant medications
- IP accountability
- SGI
- CGI-I (compared to Day 0)
- Patient most bothersome symptom, Question 2
- QMG
- 3TUG

12 DATA QUALITY ASSURANCE

Catalyst personnel or designee(s) will visit the study site before inititation of the study to preview with the site personnel information about the IP, protocol and other regulatory document requirements, any applicable randomization preocedures, source document requirements, CRFs, monitoring requirements, and procedures for reporting AEs, including SAEs.

Page 52

At visits during and after the study, a CRA will monitor the site for compliance with regulatory documentation. Data quality control and analysis will be performed by Catalyst, or designee, based on a predefined plan.

13 STATISTICAL METHODS AND DETERMINATION OF SAMPLE SIZE

13.1 Determination of Sample Size

For Change From Baseline in QMG Scores, a between-treatment difference of -3.5 and a standard deviation at most 3, a sample size of at least 24 patients will provide power of at least 80% for a 0.05 level test. Similarly, for Change From Baseline in SGI Scores, a between-treatment difference of -2.1 and a standard deviation at most 2, a sample size of at least 26 patients will provide power of 80% for a 0.05 level test. Thus a total sample size of 26 patients, equally randomized to two treatment sequences, will provide power of at least 80% for each of the two co-primary endpoints.

13.2 Patient Populations

Analyses will be presented for

- Safety Population: This population consists of all randomized patients who receive at least 1 dose of IP (amifampridine or placebo)
- Full Analysis Set (FAS): This population consists of all randomized patients who receive at least 1 dose of IP (amifampridine or placebo) and have at least one post-treatment efficacy assessment.
- Per Protocol (PP): This population is a subset of the FAS population, excluding patients with major protocol deviations. The PP population will include all patients who:
 - Have no major protocol deviations or inclusion/exclusion criteria deviations that might potentially affect efficacy, and
 - Patients who took at least 80% of the required treatment doses and remained enrolled for at least 4 days.

Evaluations obtained at the time of discontinuation will be included in the analyses. Patients who discontinue with no post-randomization data will be excluded from all efficacy analyses but will be included in the safety analyses.

Page 53

13.3 Safety Analysis

Safety analyses will be conducted on the Safety Population. The safety analysis will be descriptive and will be presented using observed data only.

All AEs will be coded using the Medical Dictionary for Regulatory Activities (MedDRA). Only TEAEs will be included in the safety analysis. The incidence of TEAEs will be summarized by system organ class, preferred term, relationship to IP, and severity by treatment. Deaths, SAEs, and AEs leading to premature discontinuation will be listed. Vital signs, ECGs, physical examination data, and concomitant medications will also be summarized. Routine laboratory assessments will not be performed. Laboratory evaluations, if performed, will be listed.

13.4 Efficacy Analysis

Efficacy analyses will be conducted on the FAS and PP populations, with the FAS population serving as the primary analysis set. For each efficacy variable with a corresponding assessment at Baseline, Change From Baseline (CFB) will be computed as the post-treatment result minus the Baseline result. The post-treatment result will be the result obtained on Day 4, unless the subject discontinued treatment early, in which case the post-treatment result may be obtained at an earlier time point. For statistical tests, two-sided P values <0.05 will be considered as statistically significant.

Summary statistics for QMG score and the corresponding CFB will be presented by treatment. The analysis of CFB for Total QMG Score is a coprimary efficacy endpoint and analysis will be performed by fitting a fixed effects linear model to the data with CFB as the response. The model will include terms for treatment and QMG at Baseline. The following test comparing the least squares (LS) means will be conducted to evaluate the treatment effect:

HA,0: LSMeanQMG(A) = LSMeanQMG(P) vs. HA,1: $LSMeanQMG(A) \neq LSMeanQMG(P)$,

where LSMeanQMG(A) is the QMG LS mean of the amifampridine treatment group and LSMeanQMG(P) is the QMG LS mean of the placebo treatment group.

The raw scores and CFB for each item of QMG will be summarized by treatment. Between-treatment comparisons with respect to CFB for Right arm outstretched, Left arm outstretched, Right leg outstretched, and Left leg outstretched will be performed using a GLM with terms for treatment, QMG at Baseline and treatment duration (in days).

Page 54

Summary statistics for SGI score and the corresponding CFB will be presented by treatment. The analysis of CFB for SGI is a coprimary efficacy endpoint and analysis will be performed by fitting a fixed effects linear model to the data with CFB as the response. The model will include terms for treatment and SGI at Baseline. The following test comparing the LS means will be conducted to evaluate the treatment effect:

HB,0: LSMeanSGI(A) = LSMeanSGI(P) vs. HB,1: LSMeanSGI(A) \neq LSMeanSGI(P),

where LSMeanSGI(A) is the SGI LS mean of the amifampridine treatment group and LSMeanSGI(P) is the SGI LS mean of the placebo treatment group.

A sensitivity analysis of the coprimary endpoints will be conducted to evaluate the patterns of early treatment discontinuation. For each coprimary endpoint, a randomization test will be conducted to determine if the results from the primary analysis are supported. The randomization test is an alternative to a full permutation, and will evaluate the fixed effects model specified above using permutations of the treatment group assignments. If early discontinuations are not associated with treatment, then it is expected that the p-value resulting from the randomization test will yield the same statistical interpretation as the p-value resulting from the primary analysis.

The proportion of patients with at least 20% increase in average time for 3TUG will be summarized by treatment and analyzed using Fisher's Exact Test. The assessment of the Patient's Most Bothersome Symptom will be summarized by treatment and analyzed using a Wilcoxon Rank Sum Test.

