The raw scores and CFB for each item of QMG will be summarized by treatment. Between-treatment comparisons with respect to CFB for Right arm outstretched, Left arm outstretched, Right leg outstretched, and Left leg outstretched will be performed using a fixed effects linear model with terms for treatment and OMG at Baseline.

Summary statistics for SGI score and the corresponding CFB will be presented by treatment. The analysis of CFB for SGI is a coprimary efficacy endpoint and analysis will be performed by fitting a fixed effects linear model to the data with CFB as the response. The model will include terms for treatment and SGI at Baseline. A test comparing the LS means will be conducted to evaluate the treatment effect.

Page 8

Table of Contents

1.	PROCEDURES IN CASE OF AN EMERGENCY				
2	SYNOPSIS				
3	LIST OF ABBREVIATIONS AND DEFINITIONS OF TERMS				
4	ETH	ETHICS			
	4.1	Institu	tional Review Board / Independent Ethics Committee	14	
	4.2	Ethica	l Conduct of Study	15	
	4.3	Patient	t Information and Informed Consent	15	
5	INV	ESTIG	ATORS AND STUDY ADMINISTRATIVE STRUCTURE	16	
6	INT	RODUC	CTION	17	
	6.1	Diseas	e Background	17	
	6.2	Amifa	mpridine	19	
	6.3	Noncli	inical Studies	20	
		6.3.1	Carcinogenicity Study	21	
	6.4	Previo	us Clinical Studies	22	
		6.4.1	Amifampridine Phosphate in Healthy Subjects	22	
		6.4.2	Efficacy of Amifampridine in LEMS	24	
		6.4.3	Safety of Amifampridine and Amifampridine Phosphate	25	
		6.4.4	Overall Risks and Benefits	27	
		6.4.5	Study Rationale	27	
7	STU	JDY OB	BJECTIVES	28	
	7.1	Primar	y Objectives	28	
8	INV	ESTIGA	ATIONAL PLAN	28	
	8.1	Overal	Il Study Design and Plan	28	
	8.2	Selecti	ion of Study Population	31	
		8.2.1	Inclusion Criteria	31	
		8.2.2	Exclusion Criteria	31	
		8.2.3	Removal of Patients from Treatment or Assessment	32	
		8.2.4	Patient Identification and Randomization	33	
		8.2.5	Re-screening	33	
	8.3	Treatn	nents	33	
		8.3.1	Treatments Administered	33	
		8.3.2	Identity of Investigational Product	34	

		8.3.3	Directions for Administration	35
		8.3.4	Method of Assigning Patients to Treatment Groups	36
		8.3.5	Selection of Doses Used in the Study	36
		8.3.6	Blinding	37
		8.3.7	Treatment Compliance	37
		8.3.8	Investigational Product Accountability	37
		8.3.9	Return and Disposition of Clinical Supplies	37
	8.4	Prior a	nd Concomitant Medications	37
	8.5	Dietary	y or Other Protocol Restrictions	38
		8.5.1	Dietary Restrictions	38
		8.5.2	Contraception	38
	8.6	Safety	Variables	38
		8.6.1	Adverse Events	39

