Descriptive statistics for Day 0, Day 4, and CFB for the sum of the QMG scores for Right arm outstretched, Left arm outstretched, Right leg outstretched, and Left leg outstretched will be presented by treatment. As was described in section 4.2.1, summary statistics will be presented for each of these for individual domains. The CFB for each of these four individual domains, and for the sum of these four domains, will be performed by fitting a fixed effects linear model to the data with CFB as the response. The model will include terms for treatment and QMG score of the respective individual domain, or sum of these four domains, as applicable, at Baseline. The following test comparing the least squares (LS) means will be conducted to evaluate the treatment effect:

 $\begin{array}{l} H_{C,0} : LSMeanQMG(A) = LSMeanQMG(P) \\ & VS. \\ H_{C,1} : LSMeanQMG(A) \neq LSMeanQMG(P), \end{array}$

where LSMeanQMG(A) is the QMG LS mean of the amifampridine treatment group and LSMeanQMG(P) is the QMG LS mean of the placebo treatment group for each individual QMG domain described above, or sum of these 4 domains. A sensitivity analysis by a randomization test for the QMG limb domain analyses is not required.

All secondary and exploratory efficacy data will be listed as shown in Appendix B.

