P-value for Between-Treatment Difference in LS Means	XXX	

^a CFB for QMG total score was modeled as the response, with fixed effects terms for treatment and QMG at Baseline. Table Creation Date: (DD-MMM-YYYY) xxxxxx.sas Source Listing: Data Listing 14

Table 15. QMG Item Scores CFB Analysis Catalyst Pharmaceuticals, Inc. - LMS-003 FAS Population (N=xxx)

QMG Item	Statistic ^a	Amifampridine	Placebo
*****	n	XXX	XXX
	Least Squares (LS) Mean of Change from Baseline (CFB)	XXX	XXX
	Between-Treatment Difference in LS Means	XXX	
	95% CI for Between-Treatment Difference in LS Means	(xxx, xxx)	
	P-value for Between-Treatment Difference in LS Means	XXX	

^a CFB for QMG item score was modeled as the response, with fixed effects terms for treatment and QMG at Baseline. A separate model was run for each QMG item. Table Creation Date: (DD-MMM-YYYY) Source Program: xxxxxxx.sas Source Listing: Data Listing 14

Table 17. SGI Score Summary Statistics by Time Point Catalyst Pharmaceuticals, Inc. - LMS-003 FAS Population (N=xxx)

Treatment	Time Point ^a	Data Type ^b	Mean	Std Dev	n	Min	Max	Median
Amifampridine	Day 0 (Baseline) Post-Baseline	RAW RAW CFB	XXX XXX XXX	XXX XXX XXX	XXX XXX XXX	XXX XXX XXX	XXX XXX XXX	XXX XXX XXX
Placebo	Day O (Baseline) Post-Baseline	RAW RAW CFB	XXX XXX XXX	XXX XXX XXX	XXX XXX XXX	XXX XXX XXX	XXX XXX XXX	XXX XXX XXX

^a The post-treatment result will be the result obtained on Day 4, unless the subject discontinued treatment early, in which case the post-treatment result may be obtained at an earlier time point. ^b RAW = observed data entered in the database; CFB = change from baseline. Table Creation Date: (DD-MMM-YYYY)

Source Program: xxxxxx.sas

Source Listing: Data Listing 13

Table 19. SGI Score Summary Statistics by Time Point and Dose Group Catalyst Pharmaceuticals, Inc. - LMS-003 FAS Population (N=xxx)

					Std				
Treatment	Dose Group	Time Point ^a	Data Type ^b	Mean	Dev	n	Min	Max	Median
Amifampridine									
	Low Dose (< 60mg/day)	Day 0 (Baseline)	RAW	XXX	XXX	XXX	XXX	XXX	XXX
		Post-Baseline	RAW	XXX	XXX	XXX	XXX	XXX	XXX
			CFB	XXX	XXX	XXX	XXX	XXX	XXX
	High Dose (> 60mg/day)	Day 0 (Baseline)	RAW	XXX	XXX	XXX	XXX	XXX	XXX
		Post-Baseline	RAW	XXX	XXX	XXX	XXX	XXX	XXX
			CFB	XXX	XXX	XXX	XXX	XXX	XXX
	All Doses	Day 0 (Baseline)	RAW	XXX	XXX	XXX	XXX	XXX	XXX
		Post-Baseline	RAW	XXX	XXX	XXX	XXX	XXX	XXX
			CFB	XXX	XXX	XXX	XXX	XXX	XXX
Placebo									
	Low Dose (< 60mg/day)	Day O (Baseline)	RAW	XXX	XXX	XXX	XXX	XXX	XXX

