
^a The post-treatment result will be the result obtained on Day 4, unless the subject discontinued treatment early, in which case the post-treatment result may be obtained at an earlier time point.

^b RAW = observed data entered in the database; CFB = change from baseline.

Table Creation Date: (DD-MMM-YYYY)

Source Program: xxxxxx.sas

Source Listing: Data Listing 14

Table 39. Limb Domain Specific QMG Total Score CFB Analysis Catalyst Pharmaceuticals, Inc. - LMS-003 FAS Population (N=xxx)

Limb Domain	Statistic ^a	Amifampridine	Placebo
Left Arm Outstretched	n	XXX	XXX
	Least Squares (LS) Mean of Change from Baseline (CFB)	XXX	XXX
	Between-Treatment Difference in LS Means	XXX	
	95% CI for Between-Treatment Difference in LS Means	(XXX, XXX)	
	P-value for Between-Treatment Difference in LS Means	XXX	
Right Arm Outstretched	n	XXX	XXX
	Least Squares (LS) Mean of Change from Baseline (CFB)	XXX	XXX
	Between-Treatment Difference in LS Means	XXX	
	95% CI for Between-Treatment Difference in LS Means	(XXX, XXX)	
	P-value for Between-Treatment Difference in LS Means	XXX	
Left Leg Outstretched	n	XXX	XXX
	Least Squares (LS) Mean of Change from Baseline (CFB)	XXX	XXX
	Between-Treatment Difference in LS Means	XXX	
	95% CI for Between-Treatment Difference in LS Means	(XXX, XXX)	
	P-value for Between-Treatment Difference in LS Means	XXX	
Right Leg Outstretched	n	XXX	XXX
	Least Squares (LS) Mean of Change from Baseline (CFB)	XXX	XXX
	Between-Treatment Difference in LS Means	XXX	
	95% CI for Between-Treatment Difference in LS Means	(XXX, XXX)	
	P-value for Between-Treatment Difference in LS Means	XXX	
Total of Regions ^b	n	XXX	XXX
	Least Squares (LS) Mean of Change from Baseline (CFB)	XXX	XXX
	Between-Treatment Difference in LS Means	XXX	
	95% CI for Between-Treatment Difference in LS Means	(XXX, XXX)	
	P-value for Between-Treatment Difference in LS Means	XXX	

 $^{\rm a}$ CFB for QMG score was modeled as the response, with fixed effects terms for treatment and QMG at Baseline. $^{\rm b}$ Total is the CFB of the sum of the four regions listed above.

Table Creation Date: (DD-MMM-YYYY)

xxxxxxx.sas

Source Listing: Data Listing 14

Table 41. Number and Percent of Subjects with Treatment Emergent Adverse Events Catalyst Pharmaceuticals, Inc. - LMS-003 Safety Population (N=xxx)

Adverse Event Category ^a :	Amifampridine	Placebo	Overall
	(N=xxx)	(N=xxx)	(N=xxx)
Total Number of Treatment Emergent Adverse Events (TEAEs)	XXX	xxx	XXX

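### The protocol and the SAP name different covariates for the exploratory QMG limb-item comparisons, and the SAP's Table 39 footnote does not match its own text

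*Protocol*

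**What the plan says.** Four places specify the limb-item model.

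- **Protocol 13.4:** the comparisons "will be performed using a GLM with terms for treatment, QMG at Baseline", and the sentence goes on to add treatment duration in days as a third term. Just above, the model for the co-primary Total QMG score is described in the same terms but without duration: "The model will include terms for treatment and QMG at Baseline".
- **Protocol synopsis:** "fixed effects linear model with terms for treatment and OMG at Baseline". I take the misprinted abbreviation to be QMG. There is no duration term.
- **SAP 4.2.2, QMG Limb Domains:** treatment and "QMG score of the respective individual domain, or sum of these four domains, as applicable, at Baseline". There is no duration term. The SAP also adds a test of the four-item sum, which the protocol does not mention.
- **SAP Appendix B, Table 39 footnote a**, the shell that reports these tests: "CFB for QMG score was modeled as the response, with fixed effects terms for treatment and QMG at Baseline".

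The Table 15 shell carries a similar footnote for item scores: "CFB for QMG item score was modeled as the response, with fixed effects terms for treatment and QMG at Baseline". SAP 4.1.2 classes the limb domains as exploratory.

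**The concern.** Table 39 will report LS means, confidence intervals and p-values for five comparisons: four limb items and their sum. The covariate set affects every one of them, and the plan does not fix it.

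In Protocol 13.4, *QMG at Baseline* is first the covariate for the total score and is then reused unchanged for single items. Read literally, the change in an item graded 0 to 3 is adjusted for a 13-item total in which 12 components are other items. Change in an item depends on where that item starts, since grade 3 cannot worsen and grade 0 cannot improve. The total captures that only in part, so with 13 or 14 patients per arm a chance imbalance in the item's own Day 0 grade may stay partly unadjusted.

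The duration term is a second conflict in the same sentence. Duration is observed after randomisation. Protocol 8.2.3 lets patients who worsen leave blinded treatment early, so duration may itself reflect treatment. Neither the synopsis nor SAP 4.2.2 includes it.

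Two specifications for one test also leave room for a choice after unblinding, and a Table 39 footnote that may describe a model other than the one fitted.

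**Working it through.** **1. Texts side by side**

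| Source | Baseline covariate | Duration term |
|---|---|---|
| Protocol 13.4 | QMG at Baseline | yes |
| Protocol synopsis | QMG at Baseline | no |
| SAP 4.2.2 | own item, or four-item sum | no |
| SAP Table 39 footnote | QMG at Baseline | no |

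The mismatch is confirmed from the text alone.

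**2. Size of the effect.** The plan states no SD, correlation or power for any limb item, so there is no figure to reproduce and every input on variability below is an assumption. From the documents I use only the 13 items graded 0 to 3 (Protocol Appendix 1), 1:1 allocation, N=26 (Protocol 13.1) or about 28 (Protocol 8.1), and the two-sided 0.05 level.

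*Closed form.* Let an item have equal variance (set to 1) at both visits, Day 0 to Day 4 correlation ρ, and correlation r with the baseline total. Let the total inform Day 4 only through the item.

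- Residual variance of change given own baseline: 1 − ρ².
- Residual variance of change given total baseline: 2(1 − ρ) − (1 − ρ)²r² = (1 − ρ)[2 − (1 − ρ)r²].
- SE ratio, total/own = √{[2 − (1 − ρ)r²]/(1 + ρ)}.

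For example, with ρ = 0.5 and r = 0.5 the ratio is √(1.875/1.5) = 1.118. With ρ = 0.8 and r = 0.7 it is √(1.902/1.8) = 1.028.

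| ρ | r=0.3 | r=0.5 | r=0.7 | r=0.9 |
|---|---|---|---|---|
| 0.3 | 1.221 | 1.185 | 1.129 | 1.050 |
| 0.5 | 1.142 | 1.118 | 1.082 | 1.031 |
| 0.7 | 1.077 | 1.064 | 1.044 | 1.017 |
| 0.8 | 1.049 | 1.041 | 1.028 | 1.011 |
| 0.9 | 1.024 | 1.020 | 1.013 | 1.005 |

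*Simulation.* Thirteen correlated items were cut to grades 0 to 3, with N=26 and 28, between-item correlation 0.2, 0.5 and 0.8, and 2,500 trials per scenario. Change in one limb item was fitted on treatment plus own baseline, and on treatment plus total baseline. Ranges are across N and between-item correlation.

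| Latent retest correlation | SE ratio, total/own | Power, own | Power, total | p<0.05 call differs |
|---|---|---|---|---|
| 0.5 | 1.14–1.17 | 41–45% | 33–36% | 17–18% |
| 0.7 | 1.07–1.10 | 50–55% | 45–49% | 14–15% |
| 0.9 | 1.01–1.04 | 74–79% | 72–78% | 7–9% |

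The mean treatment difference was about −0.61 grade under both models, and the two means never differed by more than 0.005 in any scenario. Within a single trial the two estimates differed by 0.05 to 0.16 grade on average.

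*Counter-case.* With N=28, items left continuous, and Day 4 also depending directly on a shared severity factor with weight 0, 0.2, 0.4 or 0.6, the SE ratio was 1.04, 0.94, 0.82 and 0.73. The total-adjusted model then becomes the more precise one.

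These runs compare the two baseline covariates only. None includes the duration term, so they do not quantify the full Protocol 13.4 model.

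**The case against.** The strongest reply is that SAP 4.2.2 is the most specific text on these tests and settles the covariate, leaving only loose wording elsewhere. That largely stands and is why severity is low. It does not dispose of the point, because the protocol says something else and the SAP's own shell does not carry the SAP wording.

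A reader might infer more than the documents support, in three ways.

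- **That the shells definitely adjust for the total score.** No text says *total* for the limb items. Table 39 pairs change in QMG score with QMG at Baseline, which could mean the baseline of whichever score is modelled. Table 21 names QMG baseline for the SGI model, although SAP 4.2.1 specifies SGI at Baseline, which suggests copied footnotes. The Amendment 2 log shows that wording about the corresponding baseline assessment gave way to *QMG at Baseline*, but this could be shorthand or a deliberate change.
- **That Table 15 is a second limb-item model.** Limb inference sits in Table 39, the companion Table 9 excludes limb items, and SAP 4.2.1 rules out inference on the other items. Table 15's problem is unclear scope.
- **That the protocol covariate gives a different and noisier effect.** Under randomisation both models target the same mean difference, and only the realised estimate and p-value change. The precision loss rests on correlations the documents do not give, is small when items are stable over four days, and can reverse. The floor-and-ceiling argument is also only partial: a linear own-baseline term does not remove the bounds, and the total contains the item.

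**Conclusion.** The inconsistency holds: the limb-item comparisons have conflicting covariate rules between the protocol and SAP 4.2.2, on both the baseline score and the duration term, and the Table 39 footnote does not state the SAP 4.2.2 model.

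If the protocol phrase means the total score, the cost is usually a modest loss of precision: an SE about 0.5% to 22% larger in the closed form and 1% to 17% larger in the graded simulation. It is only about 0.5% to 5% in the closed form when ρ is 0.8 or 0.9. This assumes that Day 4 does not depend strongly on overall severity beyond the item's own baseline. The firmer consequence is that the p<0.05 call can change with the model chosen, in about 7% to 18% of simulated trials, and this matters whichever model is more precise.

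Severity is low. The endpoint is exploratory, and the co-primary models in Protocol 13.4 and SAP 4.2.1 agree with each other and are not touched.

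**What to change.** - **Protocol 13.4 and synopsis:** for the four limb items, replace *QMG at Baseline* with *the baseline score of the respective item*.
- **Protocol 13.4:** delete the treatment-duration term from the limb-item sentence, so that it matches SAP 4.2.2 and the synopsis.
- **SAP Table 39/40 footnotes:** state *fixed effects terms for treatment and the baseline score of the respective domain (or of the four-domain sum)*.
- **SAP Tables 15/16:** say which items they cover. If they cover non-limb items, reconcile them with SAP 4.2.1, which allows no inference there. If any model is kept, use the same corrected footnote.

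The cost is a wording change, made before unblinding. It needs no new data and no extra patients, because the item scores are already collected on Day 0.
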